#### **9.5 Registration on ClinicalTrials.gov**

A description of this study will be available on <http://www.ClinicalTrials.gov>.

#### **9.6 Future Use of Stored Specimens and Other Identifiable Data**

All specimens will include a research study identifier but otherwise will be de-identified. Specimens remaining after study analysis will be stored for analysis in future related protocols. The use of these samples will be described in those protocols and requests will be routed through proper institutional and IRB channel for approval.

## 10 STATISTICAL CONSIDERATIONS

No previous data exists for estimating the potential magnitude of correlation of biomarkers from the 1-hour EST with other outcome variables for this power analysis. We want to have sufficient power to detect a significant correlation if the true underlying correlation is 0.45 or greater, corresponding a medium to large effect size by Cohen's operational cutoff. In this case, a sample of 40 is required to ensure 80% chance at 5% significance to detect significant correlation between a biomarker and an outcome variable.

Correlation of each biomarker level from 1 hour string test with PEESS symptom score, EREFS histopathological score or luminal diameter measured by EndoFlip at 50 mmHg pressure will be analyzed using Spearman correlation analysis. Wilcoxon rank sum test will be used to compare the difference in biomarker level between patients with different endoscopic appearance (e.g. Rings+/- Furrows + Stricture vs. Rings+/- Furrows vs. None of Rings, Furrows or Stricture). Multiple linear regression (MLR) will be used to examine the above relationship while adjusting for other covariates such as age and gender of patients. Log transformation will be used for biomarker in MLR.

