## LIST OF ABBREVIATIONS

*{Please add all disease or study-specific abbreviations/acronyms in this section. Modify this list as needed for your particular study and remove abbreviations that are not used in the document.}*

AE	Adverse Event/Adverse Experience
CFR	Code of Federal Regulations
CHCO	Children's Hospital Colorado
CHOP	Children's Hospital of Philadelphia
CRF	Case Report Form
DCC	Data Coordinating Center
DSMO	Data and Safety Monitoring Officer
EOE	Eosinophilic Esophagitis
EREFs	Endoscopic Reference System
EST	Esophageal String Test
GCP	Good Clinical Practice
HIPAA	Health Insurance Portability and Accountability Act
ICF	Informed Consent Form
ICH	International Conference on Harmonisation
IRB	Institutional Review Board
ISM	Independent Safety Monitor
MOP	Manual of Procedures
N	Number (typically refers to participants)
NIH	National Institutes of Health
OHRP	Office for Human Research Protections
OHSR	Office of Human Subjects Research
PEESS	Pediatric Eosinophilic Esophagitis Symptom Scores
PI	Principal Investigator
QA	Quality Assurance
QC	Quality Control
SAE	Serious Adverse Event/Serious Adverse Experience
SOP	Standard Operating Procedure
US	United States

Title:	Use of Esophageal String Test to understand symptoms, inflammation and function in eosinophilic esophagitis
Overview:	Presently, the only method available to monitor disease activity in Eosinophilic Esophagitis is endoscopy with pathological review of biopsies. The overall goal of this study is to determine the ability of the Esophageal String Test (EST), a minimally invasive capsule based technology, to measure disease activity in children with EoE.
Objectives:	
Primary Aim: Do eosinophil proteins captured by the EST correlate with symptoms related to pediatric EoE?
 
Secondary Aim 1: Do eosinophil proteins captured by the EST correlate with the markers of EoE pathogenesis?
 
Secondary Aim 2: Do eosinophil proteins captured by the EST correlate with a measure of esophageal function?

Population:	40 subjects: males and females, ages 7-18 years old undergoing upper endoscopy for monitoring of EoE or for symptoms of esophageal dysfunction concerning for EoE
Study Sites:	
Lead Site: Children's Hospital of Colorado
 
Recruitment Site: Children's Hospital of Philadelphia
 
Clinical Laboratory: University of Illinois, Chicago

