### 3 STUDY DESIGN

When children are scheduled to undergo an endoscopy, research assistants will contact the family to arrange for the EST to be performed within one week of the endoscopy as previously described (REF). Prior to swallowing the EST, the patient will complete the PEES form to assess symptoms. The string will be left in place for 1 hour and then removed. The endoscopy and EREFs and EndoFLIP will be performed as previously described (2). Endoscopic severity: Endoscopic esophageal appearances will be scored using a validated EoE scoring system (EREFS). Five features of EoE will be scored: Edema (0-1), Rings (0-3) Exudates (0-2), Furrows (0-1), Stricture (0-1). Results will be reported as an inflammatory score (edema, exudates, furrows) and fibrostenotic score (rings, stricture). Functional Luminal Imaging Probe (FLIP): After endoscopic visualization, the FLIP, a 16 cm probe (Crospon) will be placed transorally and positioned 3 cm distal to the lower esophageal sphincter. Esophageal cross sectional areas and intrabag pressure will be measured during stepwise distensions beginning with 5 mL and increasing to a maximum of 70mL or intrabag pressure of 50 mmHg is achieved, whichever comes first. FLIP is FDA-approved without age restriction and its use has been approved by our IRBs previously. Primary results will be reported as distensibility plateau (mm).

EST and biopsy samples: The EST will be placed in a labeled tube and frozen until analysis as below. Four mucosal biopsies will be obtained from the distal esophagus for protein (3) and histological (1 biopsy) analysis. Samples for protein analysis will be snap frozen for batch processing and assessment. Samples for histological analysis will be paraffin embedded and cut into 5 $\mu$ M sections for batch staining.

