### **4.1 Subject Inclusion Criteria**

In order to be eligible to participate in this study, an individual must meet all of the following criteria:

- Provide signed and dated informed consent form.
- Willing to comply with all study procedures and be available for the duration of the study.
- Male or female, aged 7 to 18 years old, inclusive
- Undergoing upper Endoscopy with biopsy for clinical care at CHCO or CHOP
- Current or historical diagnosis of EoE, or suspected of having EoE

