**Functional Luminal Imaging Probe (FLIP):** After endoscopic visualization, the FLIP, a 16 cm probe (Crospon) will be placed transorally and positioned 3 cm distal to the lower esophageal sphincter. Esophageal cross sectional areas and intrabag pressure will be measured during stepwise distensions beginning with 5 mL and increasing to a maximum of 70 mL or intrabag pressure of 50mmHg is achieved, whichever comes first. To prevent unintended dilation of a stiff esophagus, infusion will stop and alarm message will sound if intrabag pressure exceeds 60 mm Hg. Raw data will be exported to EndoFLIP Analytics and will be filtered to remove measurements during esophageal contractions and vascular and respiratory artifacts. A polynomial regression method to identify pressure to cross sectional area relationships will be used to determine outcomes, narrowest cross sectional area, and distensibility plateau. FLIP is FDA-approved without age restriction and its use has been approved by our IRBs previously. Primary results will be reported as distensibility plateau (mm).

**EST and biopsy samples:** The EST will be placed in a labeled tube and frozen until analysis as below. Four mucosal biopsies will be obtained from the distal esophagus for protein (3 biopsies) and histological (1 biopsy) analysis. Samples for protein analysis will be snap frozen for batch processing and assessment. Samples for histological analysis will be paraffin embedded and cut into 5 $\mu$ M sections for batch staining.

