### 6.2 Lab Procedures

EST samples and corresponding biopsies will be shipped in 3 month intervals to [name] at the University of Illinois, Chicago. EST sample processing and analysis- EST samples will be thawed (previously harvested and frozen in extraction buffer with protease inhibitors) on ice and vortexed for 1 min at maximum vortex speed. Biomashers will be used to separate the string from the EST sample following manufacturer instructions to homogenize the sample, centrifuge the filter column (1min/13,400 rpm/+4°C) and collect the flow through. The EST eluates are aliquoted and stored at -80°C until used in biomarker assays. ELISAs for selected eosinophil biomarkers including MBP1 and CLC/Gal-10 (in house ELISAs at UIC), and commercial ELISAs for EPX and EDN will be performed as per manufacturer instructions (2). Measurement of non-eosinophil protein biomarkers including CCL24, CCL26, TSLP, Lox5, EMSY, IL-13, periostin and others will be done by commercial ELISAs and nanostring methods (2,16,17). Results will be reported as mass amount of protein/ml after adjusting for sample dilution factors.

1. Histopathological scores- Cut paraffin embedded samples will be assessed and scored for each of EoEHSS(4), EPX (5) and EMT (6) as previously described.
2. Data capture- PEESS survey results, FLIP results, histopathology and EREFs scores and molecular readouts will be loaded into the REDCAP study database after obtained.
3. Data Analysis- In order to address our aims, we will perform the following correlation analyses.
  - a. EST protein analyte concentration vs. PEESS scores
  - b. EST protein analyte concentration vs. EREFS scores
  - c. EST protein analyte concentration vs. EoEHSS scores
  - d. EST protein analyte concentration vs. EPX scores
  - e. EST protein analyte concentration vs. EMT scores
  - f. EST protein analyte concentration vs. nano-string biomarkers
  - g. EST protein analyte concentration vs. EndoFLIP numerical values

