Correlation of biomarkers from 1 hr ESTs with PEESS symptom score or histology scores. Analysis of variance or its non-parametric counterpart will be used to compare the differences in biomarkers between patients with different endoscopic appearance (e.g. Rings+/- Furrows + Stricture vs. Rings+/- Furrows vs. None of Rings, Furrows or Stricture). The semi partial correlation of biomarker level from string test with cross sectional area at 40 mmHg pressure, a metric of extensibility from FLIP test, will be examined using multiple linear regression (MLR) while adjusting for age of patient. MLR will also be used to examine the association of the outcomes with multiple biomarkers. No adjustment for comparisons of multiple outcomes will be applied in order to preserve some power for this study.

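### Secondary Aim 2 (esophageal function): the FLIP result called primary is named in no analysis, and sections 6.2 and 10 analyse two other FLIP metrics without saying which metric, test or covariate set answers the aim.

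*Combined protocol and SAP*

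**What the plan says.** The synopsis asks, as Secondary Aim 2: "Do eosinophil proteins captured by the EST correlate with a measure of esophageal function". Section 2.1 calls this Specific Aim 3 and refers only to distensibility measurements in general.

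Sections 3 and 6.1 both state: "Primary results will be reported as distensibility plateau (mm". Section 6.1 adds that a polynomial fit of pressure against cross sectional area "will be used to determine outcomes, narrowest cross sectional area, and distensibility plateau".

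The analysis text then uses other quantities:

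- Section 6.2, analysis list, item g: "EST protein analyte concentration vs. EndoFLIP numerical values", with no metric named.
- Section 6.2, text after the list: "The semi partial correlation of biomarker level from string test with cross sectional area at 40 mmHg pressure", by multiple linear regression (MLR) adjusted for age. The same paragraph declines any adjustment for multiple outcomes.
- Section 10: "luminal diameter measured by EndoFlip at 50 mmHg pressure will be analyzed using Spearman correlation analysis", then MLR with log-transformed biomarker and an open-ended covariate list that gives age and gender as examples.

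Two design facts bear on this. Eligibility is "Male or female, aged 7 to 18 years old, inclusive", and the title of the protocol's reference 8 reports that esophageal distensibility rises with age. Distension proceeds in steps, "increasing to a maximum of 70 mL or intrabag pressure of 50mmHg is achieved, whichever comes first".

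**The concern.** Three FLIP quantities are in play for one aim: the plateau, area at 40 mmHg and diameter at 50 mmHg. The one called primary is not named in any analysis. The two that are named differ in pressure, in the first test applied and in the covariates. No sentence says which combination is the answer to the aim.

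With no multiplicity adjustment, several p-values per biomarker will exist for this aim, and the choice of which to lead with is left until after the results are known. The choice between unadjusted and age-adjusted results matters most, because the age range is wide and the protocol's own reference points to age as a determinant of distensibility. A smaller gap is that a child who reaches 70 mL first has no observed value at 50 mmHg, and no handling rule is given.

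**Working it through.** **1. The plan's own figure.** Section 10 gives N=40 for 80% power at 5% significance to detect r=0.45. Two-sided testing is assumed, since sidedness is not stated. With Fisher's z, n = v × ((1.960 + 0.842)/atanh(0.45))² + 3, and atanh(0.45) = 0.4847, so the squared term is 33.41.

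- Pearson (v=1): 36.4, so 37.
- Spearman (v=1.06): 38.4, so 39.
- Spearman (v = 1 + 0.45²/2 = 1.101): 39.8, so 40.

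N=40 therefore fits one two-sided, unadjusted Spearman test of one biomarker against one outcome. The figure is not in dispute.

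**2. Side by side.**

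| Place | FLIP metric | Method | Covariates |
|---|---|---|---|
| Sections 3 and 6.1 | Distensibility plateau (mm), called primary | none named | none named |
| Section 6.2, item g | unspecified | correlation | none named |
| Section 6.2, text | Area at 40 mmHg | semi-partial correlation from MLR | age |
| Section 10, first step | Diameter at 50 mmHg | Spearman | none |
| Section 10, second step | Diameter at 50 mmHg | MLR, log biomarker | open list, including age and gender |

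Area and diameter at the same site and pressure have the same rank order if the lumen is circular, so that difference alone would not alter a Spearman test. What remains is plateau versus fixed pressure, 40 versus 50 mmHg, and unadjusted versus age-adjusted.

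**3. Choice among metrics.** Simulation with N=40, one biomarker, no true association, normal data, and Spearman at two-sided 5% for each metric. The documents give no inter-metric correlation, so it is an assumption. Entries are the chance of at least one p<0.05, as approximate values from runs of 20,000 to 40,000 samples.

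| Inter-metric correlation | Two metrics named in the analysis text | All three |
|---|---|---|
| 0.98 | 6% | 7% |
| 0.95 | 7% | 8% |
| 0.9 | 7% | 9% |
| 0.8 | 8% | 10-11% |
| 0.7 | 8-9% | 11% |

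Allowing for simulation error, this is 6-9% for two metrics and 7-12% for three.

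**4. Choice of age adjustment.** Assume no association between biomarker and FLIP given age. The marginal correlation is then the product of the two age correlations. Both age correlations are assumptions.

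| Age-FLIP | Age-biomarker | Marginal r | Spearman rejects | MLR with age rejects |
|---|---|---|---|---|
| 0.3 | 0.2 | 0.06 | 6% | 5% |
| 0.3 | 0.3 | 0.09 | 8-9% | 5% |
| 0.5 | 0.2 | 0.10 | 9% | 5% |
| 0.5 | 0.3 | 0.15 | 14% | 5% |

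**5. Power under the planned effect.** Take r=0.45 as the marginal correlation, as section 10 does, with age unrelated to the biomarker. The age-adjusted correlation is 0.45/√(1 − b²), where b is the age-FLIP correlation. It is 0.45, 0.47 and 0.52 for b = 0, 0.3 and 0.5. Spearman power stays at 80% throughout, while MLR with age gives 84%, 88% and 94%. About 4 points of that gap come from comparing a rank test with a linear test on normal data.

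**6. Unreached 50 mmHg.** The documents do not give the share of children who reach 70 mL first, so no loss of power is calculated.

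**The case against.** The strongest reply is that this is a documentation inconsistency on one secondary aim of a correlational study that openly declines multiplicity adjustment. Much of that stands, and it limits the point in five ways.

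- A reader might infer that the plateau is excluded from analysis. The documents do not support that. Item g and section 2.1 are broad enough to include it, and the primary-results sentence sits in the device procedure text, where it may describe reporting and not the aim's endpoint. The plateau is unspecified, not ruled out.
- A reader might infer that section 10 ignores age. It does not. Both sections contain an age-adjusted model, so the 6-14% describes unadjusted Spearman read alone. What is missing is which result leads.
- The metrics may be close. The plateau is in mm, as a diameter would be, and 50 mmHg is the planned end of distension, so diameter at 50 mmHg could be its intended working form. That is why the range in step 3 runs up to 0.98, where the excess over 5% is only 1 to 2 points.
- A reader might infer that the unadjusted test is underpowered. That follows only if 0.45 is moved from the marginal to the age-adjusted correlation, which the plan does not do.
- A reader might attach a power loss to children stopped at 70 mL. Any such figure would rest on an invented share.

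What the reply does not remove is that the sections name different metrics and tests for the same aim and leave them unranked.

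**Conclusion.** The point holds as an inconsistency that should be fixed. For Secondary Aim 2 the plan fixes neither the FLIP metric, nor the test, nor the covariate set, and the metric it calls primary is named in no analysis.

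The false-positive cost per biomarker is modest for the choice of metric (6-9% over two, 7-12% over three, at inter-metric correlation 0.98 to 0.7). It can be larger for the choice of age adjustment (6-14% against 5%, if age correlates 0.3-0.5 with FLIP and 0.2-0.3 with the biomarker). All these correlations are assumptions, with normal data and two-sided tests. There is no shortfall against the stated 80% power, N=40 stands, and the primary symptom aim is not touched. The 50 mmHg gap is real but of unknown size.

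**What to change.** Before EST and FLIP data are linked:

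1. Reconcile sections 3, 6.1, 6.2 and 10 so that one FLIP metric is the main outcome of this aim. If the sponsor keeps the plateau as primary, fix its derivation from the polynomial fit in advance. Label the other FLIP metrics secondary.
2. Name the already planned MLR with log biomarker and age as the main analysis, reporting the semi-partial correlation with its confidence interval. Keep unadjusted Spearman and the model with age and gender as supportive.
3. For every FLIP metric, the plateau included, state how children stopped at 70 mL before the needed pressure are handled in the analysis: do not extrapolate beyond the observed pressure, report how many there are, and give results both with them excluded and with the last observed step used.

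The cost is wording and a little extra analysis, since age and the pressure-area data are already collected. The downside is that section 10's Spearman test, the one N=40 fits, becomes supportive for this aim. The inflation limits are not changed.

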## 6 STUDY PROCEDURES/ EVALUATIONS

### 6.1 Study Procedures

When children are scheduled to undergo an endoscopy, research assistants will contact the family to arrange for the EST to be performed within one week of the endoscopy. Prior to swallowing the EST, the patient will complete the PEESS form to assess symptoms. The string will be left in place for 1 hour, removed. The EST will be removed from the subject at least 2 hours before the scheduled upper endoscopy time to align with NPO guidelines for upper endoscopy. The endoscopy and EREFs and EndoFLIP will be performed per clinical guidelines and procedures for EndoFLIP (described below).

**Pediatric EoE Symptom Score (PEESS):** PEESSv2.0 is a validated pediatric PRO that contains patient and parent proxy instruments that can be easily understood. Scoring is based on two domains that evaluate frequency and severity of the symptoms reported by the patient (see Appendix 1). PEESS Score v2.0 will be used to assess EoE symptoms. The PEESSv2.0 Children and Teens Report (8-18) is intended for children ages 8-18 years old to complete independently. The PEESSv2.0 Parent Report for Children and Teens (2-18) is completed for all subjects by the parent.

**Endoscopic severity:** Endoscopic esophageal appearances will be scored using a validated EoE scoring system (EREFs). Five features of EoE will be scored: Edema (0-1), Rings (0-3) Exudates (0-2), Furrows (0-1), Stricture (0-1). Results will be reported as an inflammatory score (edema, exudates, furrows) and fibrostenotic score (rings, stricture) (see Appendix 2).

**EST Satisfaction Survey:** Following the string procedure, the subject and parent will be asked to complete a survey within 2-5 days of the endoscopy. The survey will assess symptoms/side effects after the string and endoscopy procedures, and collect information on patient preference with string versus the endoscopy.

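### The only endoscopic grouping offered leaves out edema and exudates and does not clearly place every child; exclusive, exhaustive groups should be defined before this secondary contrast is analysed

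*Combined protocol and SAP*

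**What the plan says.** Section 6.1 (and section 3 in the same terms) sets out the endoscopic scoring: "Five features of EoE will be scored: Edema (0-1), Rings (0-3) Exudates (0-2), Furrows (0-1), Stricture (0-1"). It then splits the features: "Results will be reported as an inflammatory score (edema, exudates, furrows) and fibrostenotic score (rings, stricture").

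Two analyses use endoscopy. The first is a correlation, listed in 6.2 as "EST protein analyte concentration vs. EREFS scores". Section 10 states that it "will be analyzed using Spearman correlation analysis".

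The second is a comparison of groups. Section 6.2 says: "Analysis of variance or its non-parametric counterpart will be used to compare the differences in biomarkers between patients with different endoscopic appearance". Section 10 says: "Wilcoxon rank sum test will be used to compare the difference in biomarker level between patients with different endoscopic appearance". Both sections illustrate the groups in the same way: "e.g. Rings+/- Furrows + Stricture vs. Rings+/- Furrows vs. None of Rings, Furrows or Stricture". No other grouping appears in the protocol, and neither section says which children belong to each group beyond this example.

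**The concern.** The study measures eosinophil proteins, and its premise is that these follow esophageal inflammation. The example grouping keeps both fibrostenotic features but only one of the three inflammatory ones. A child with marked exudates and edema, and no rings, furrows or stricture, would be counted with children whose esophagus looks normal. If such children carry raised protein levels, the comparator's level rises and the contrast shrinks.

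The second difficulty is that *Rings+/- Furrows* can be read in several ways, and some leave children without a group. Those children would be dropped or placed by a decision taken after the data are seen, in a study where 6.2 makes no adjustment for multiple outcomes. A weak or null group comparison would then be hard to interpret.

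**Working it through.** **The plan's own figure.** The only design figure is N = 40 for 80% power at 5% significance "if the true underlying correlation is 0.45 or greater" (section 10). Sidedness is not stated; two-sided is assumed. With Fisher's z, n = v × ((1.960 + 0.842) / atanh 0.45)² + 3, where atanh 0.45 = 0.485:

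- Pearson, v = 1: 36.4, so 37.
- Spearman, v = 1.06: 38.4, so 39.
- Spearman, v = 1 + 0.45²/2 = 1.101: 39.8, so 40.

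The figure is reproduced for a Spearman correlation. It does not size the group contrast, for which the plan states no effect, group size or power.

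**Who goes where.** Below are the eight present/absent patterns of rings (R), furrows (F) and stricture (S) under four readings of the example. A: rings required, furrows optional. B: furrows required, rings optional. C: rings and/or furrows. D: any stricture first, then any ring or furrow.

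| Pattern | A | B | C | D |
|---|---|---|---|---|
| none of the three | None | None | None | None |
| F only | no group | middle | middle | middle |
| R only | middle | no group | middle | middle |
| R + F | middle | middle | middle | middle |
| S only | no group | no group | no group | stricture |
| F + S | no group | stricture | stricture | stricture |
| R + S | stricture | no group | stricture | stricture |
| R + F + S | stricture | stricture | stricture | stricture |
| patterns without a group | 3 of 8 | 3 of 8 | 1 of 8 | 0 of 8 |

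Each pattern occurs with four combinations of edema and exudates, so the unplaced patterns number 12, 12, 4 and 0 of 2⁵ = 32. Under all four readings the 'None' group holds four of the 32 patterns, and three of those four include edema and/or exudates. These are counts of possible patterns, not of children.

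**Possible dilution (assumptions, not figures from the documents).** Let the affected group's mean exceed the unaffected mean by d, and let a fraction f of 'None' have levels like the affected group. The 'None' mean rises by f × d, so the contrast becomes d − f × d = d(1 − f). At f = 0.25 it is 0.75d; at f = 0.5 it is 0.5d.

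Section 10 names a rank test, so power was simulated for a two-sided 5% Wilcoxon test (normal data, SD 1, d = 1.0 SD, 20,000 runs per cell). The 20 vs 20 row splits all 40 children in two; 13 vs 13 is about one pair out of three equal groups (40/3 ≈ 13).

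| f | 0 | 0.1 | 0.2 | 0.3 | 0.5 |
|---|---|---|---|---|---|
| 20 vs 20 | 85% | 76% | 64% | 52% | 29% |
| 13 vs 13 | 64% | 54% | 43% | 33% | 19% |

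For d from 0.8 to 1.2 SD with 20 vs 20, power is 67–95% at f = 0 and 37–65% at f = 0.3.

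**Unplaced children.** These reduce N and do not dilute. With d = 1.0 SD, losing 10%, 20% or 30% of 40 (18, 16 or 14 per group) gives 80%, 75% or 68%, against 85%.

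**The case against.** The strongest reply is that the grouping is introduced as an example, so no wrong definition has been fixed. That stands. The fair criticism is that no final grouping exists and that the one illustration is not a sound starting point.

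A reader might infer that furrows without rings have no group. That follows only under reading A. The third group's wording suggests that rings and/or furrows may have been meant, and then furrows-only children are placed.

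A reader might also infer that the contrast is in fact diluted, or that 12 in 32 children would be lost. The documents support neither. They give no feature prevalences and no biomarker levels by feature, and the EREFS features need not occur independently.

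Edema and exudates are also analysed elsewhere, in the planned EREFS correlation. This stands too, although section 10 does not say whether the total or a sub-score is used. The correlation limits the consequence but does not repair the group comparison.

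Finally, the contrast is secondary: the primary aim concerns symptoms, and N = 40 was sized for a correlation. That lowers the stakes without removing the need for a definition.

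**Conclusion.** The point holds in a limited form. It is certain from the text that the only grouping offered omits two of the three inflammatory features, and that children with edema and/or exudates alone fall in 'None' however the example is read. It is also certain that the middle group's label is ambiguous and that several natural readings leave some children unplaced.

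A shift towards the null is possible but not shown. Its size depends on f, which must be assumed, and on those children having levels like the affected group. The effect is confined to the endoscopic-group contrast; the symptom analysis, the EREFS correlation and the sample size are untouched. It should be corrected before analysis, but it does not threaten the study's main conclusion.

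The two sections also differ on the test: section 10 names a two-group test for three listed groups, whereas 6.2 names analysis of variance or its non-parametric counterpart.

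**What to change.** Before analysis, replace the example in both 6.2 and 10 with three groups built on the protocol's own sub-scores:

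1. no EREFS feature;
2. inflammatory features only: edema, exudates or furrows, with neither rings nor stricture;
3. any fibrostenotic feature: rings or stricture.

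These place each of the 32 patterns exactly once: 1 in the first group, 2³ − 1 = 7 in the second and (2² − 1) × 2³ = 24 in the third.

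Count a feature as present if it is graded above 0 at either Appendix 2 location, and state how *Cannot Assess* is handled. Working with presence also avoids the difference between furrows scored 0–1 in 6.1 and 0–2 in Appendix 2.

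Compare the three groups with Kruskal-Wallis, the non-parametric counterpart that 6.2 allows, and keep the Wilcoxon rank sum test for pairwise follow-up only.

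The cost is a few sentences and no new data, since the Appendix 2 form already records every feature. There are two drawbacks. Stricture is no longer a separate group and would be reported descriptively. The third group also mixes children with and without inflammatory signs (3 of its 24 patterns have none), so the correlation with the inflammatory score should be read beside it.
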